Rotational stability will be assessed for each eye at least 15 minutes after lens insertion at the fitting visit, and at the 1-week follow-up visit. However, rotational stability assessed at least 15 minutes after lens insertion at the fitting visit is the primary endpoint. Rotational stability is a binary response where Y=1 if the lens stability with blinks is $\leq 5^\circ$ and Y=0 otherwise. See [REDACTED] in Appendix D for details regarding the collection of lens stability with blinks.

Clinical Study Protocol
Johnson & Johnson Vision Care, Inc.

Subjective Vision

Subjective vision will be assessed using the Contact Lens User Experience (CLUE™) questionnaire after approximately 1 week of lens wear. CLUE™ is a validated, patient-reported outcomes questionnaire to assess patient-experience attributes of soft, disposable contact lenses (comfort, vision, handling, and packaging) in a contact-lens wearing population in the US, ages 18-65. Derived CLUE™ scores using Item Response Theory (IRT) follow a normal distribution with a population average score of 60 (SD 20), where higher scores indicate a more favorable/positive response with a range of 0-120. A 5-point increase in an average CLUE™ score translates into 10% shift in the distribution of scores for population of soft contact lens.⁵

Secondary Endpoints

- CLUE Handling score at follow-up
- CLUE Comfort score at follow-up

Exploratory Endpoints

- Ability to see comfortably while driving during the day [REDACTED]
- My vision was clear enough to allow me to drive at night [REDACTED]
- Reduction in the feeling of tired eyes from using a computer or other digital device [REDACTED]

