Visit 1: Lens Fittin #1		
Step	Procedure	Details
1.21	Toric fit assessment	
Record for each eye:
 
 1. The rotational position to the nearest degree 2. Lens stability with blinks 3. Toric fit acceptability. The toric lens fit will be designated as 'unacceptable' if either: 
 a. The lens ABSOLUTE ROTATION is greater than 20 degrees b. The LENS STABILITY WITH BLINK is greater than 5 degrees 
If one or both lenses demonstrate an unacceptable toric fit, the subject will be discontinued (proceed to final evaluation).

1.22	General lens fit assessment	
The fitting characteristics of the lens in both eyes will be assessed using a slit lamp. Lens position (centration, limbal exposure, edge lift) and movement (primary and up gaze as well as push-up) will be assessed. Fit acceptability is defined as any lens that does not display the following general fit characteristics:
 
 • Limbal exposure (presence of clear comea) in any direction of gaze. • Edge lift. • Insufficient movement in all three movement assessments (primary gaze, up-gaze and push-up test). • Excessive movement in primary gaze. 
If the general fit is unacceptable for either eye, the subject will be discontinued (proceed to exit evaluation).

1.23	Spherical over-refraction	
Perform monocular spherical over-refraction using duo-chrome to refine the endpoint as described in step 1.11 (the final spherical endpoint may be determined binocularly).
 
The spherical over-refraction must be plano in both eyes to continue.
 
If a non-plano over-refraction is found in either eye, the lens(es) must be refit with the indicated change in sphere power. If the indicated lens power is not available for either eye (e.g., outside the available SKU range), the subject will be discontinued (proceed to final evaluation).

Clinical Study Protocol
Johnson & Johnson Vision Care, Inc.

Visit 1: Lens Fittin #1		
Step	Procedure	Details

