3.5	Biomicroscopy	The FDA Slit Lamp Classification Scale will be used to grade findings. If any slit lamp finding is graded as 3 or worse, the subject must be discontinued, an adverse event will be recorded, and the subject will be monitored as per the guidelines given in section 13. Should the clearance of the fluorescein need to be expedited, preservative free rewetting drops or artificial tears may be instilled.
3.6	Continuance	Verify that the subject is eligible to continue in the study.

Visit 3: Lens Fitting #2

The steps followed will be the same as those listed under Visit 1: Lens Fitting #1.

VISIT 4

Visit 4 will occur 5 to 9 days following Visit 3. Subjects must present to this visit wearing the study lenses in both eyes, and lenses must have been worn for at least 1 hour prior to the visit.

Subjects should bring their own habitual spectacles or contact lenses to this visit to wear following study lens removal.

Visit 4: Follow-Up #2

The steps followed will be the same as those listed under Visit 2: Follow-Up #1, up to and including step 2.12 'Biomicroscopy' ('Exit visual acuity' and 'Schedule next visit' will not be completed here). Additionally, a Preference Questionnaire will be completed as part of the Follow-Up PRO questionnaire (step 2.5).

Clinical Study Protocol
Johnson & Johnson Vision Care, Inc.

FINAL EVALUATION

The final evaluation will ordinarily take place immediately following the last scheduled follow-up visit per the study protocol. It may also take place at any point the subject discontinues the study or is terminated from the study.

Final Evaluation		
Ste	Procedure	Details
F.1	Subject Disposition	Indicate if the subject completed the study successfully. If the subject is discontinued from the study, indicate the reason.
F.2	Exit Refraction	Perform bare-eye subjective spherocylindrical refraction with a phoropter and record the best-corrected distance visual acuity (OD and OS) to the nearest letter. Note: This step is not necessary if the subject was exited due to screen failure.

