8.2. Withdrawal/Discontinuation from the Study

A subject will be withdrawn from the study for any of the following reasons:

- Subject withdrawal of consent.
- Subject not compliant to protocol.

Clinical Study Protocol
Johnson & Johnson Vision Care, Inc.

- Subject lost to follow-up.
- Subject no longer meets eligibility criteria (e.g. the subject becomes pregnant).
- Subject develops significant or serious adverse events necessitating discontinuation of study lens wear.
- Subjects who have experienced a Corneal Infiltrative Event (CIE).
- Investigator's clinical judgment regarding the subject safety reasons (that it is in the best interest of the subject to stop treatment).
- Subject missed any study visits
- Subject not compliant with study lens wear schedule.
- Subject not successfully dispensed due to lack of efficacy and safety including poor vision, poor comfort, or unacceptable fit.

For discontinued subjects, the Investigator will:

- Complete the current visit (scheduled or unscheduled).
- Complete the Final Evaluation, indicating the reason that the subject was discontinued from the study.
- Record the spherocylindrical refraction with best corrected distance visual acuity.
- Collect used test article(s) (worn or brought to the visit) from the subject and discard them, unless otherwise stated in section 7.2.
- Collect all unused test article(s) from the subject.
- Make arrangements for subject care, if needed, due to their study participation

Additional subjects may be enrolled if a subject discontinues from the study prematurely.

In cases where a subject is lost to follow-up, every possible effort must be made to contact the subject and determine the reason for discontinuation/withdrawal. The measures taken to follow up must be documented including two written attempts and a certified letter (or equivalent) as the final attempt.

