14.2. Sample Size Justification

This study was designed and powered to test for superiority of the test lens after 1-week of lens wear with respect to the following: distance monocular HLHC visual acuity (logMAR), subjective vision scores, toric lens orientation, and rotational stability. This study was also powered to test superiority of the test lenses with respect to grade 3 or higher slit lamp findings and percentage of eyes with acceptable lens fit. Additionally, this study was also powered to test for superiority with respect to CLUE Comfort and Handling scores after 1-week of lens wear. The described alpha adjustment is also factored into these estimations of sample size and power.

The sample size for co-prima1y efficacy endpoints was estimated to achieve a minimum statistical power of 90% for distance monocular visual acuity (logMAR), toric lens orientation, rotational stability, and CLUE Vision scores using a 2-sided type I eITor rate of 5%. Co-prima1y safety endpoints (grade 3 or higher SLFs and acceptable lens fitting) were estimated to achieve a minimum statistical power of 99% with 95% central posterior credible interval.

A summa1y of historical studies utilized in the sample size calculation are summarized in Table 7 below, while Table 8 summarizes the historical data for the test lens by endpoint.

Table 7: Historical Studies Utilized for Sample Size Calculations

Study Number	Design	Sample Size	Number in Safety	Number in PP
4	2x3	Feasibility	145	144
	2x3	Conformation	126	26

PP: Per-Protocol

Table 8: Historical Data by Endpoint - Test Lens

Endpoint Type	Endpoint	Data Type	Value
*Primary Safety	Grade 3 + SLFs (Adverse Event)	Rate	0%
	Acceptable Lens Fitting		100%
**Primaiy Efficacy	Distance Monocular Visual Acuity (logMAR)	Mean (SD)	-0.115 (0.0769)
	Absolute Toric Rotation 10°		97.5%
	Lens Stability with Blinks 5°		100%
	CLUE Vision Scores		67.4 (19.67)
**Secondary	CLUE Handling Scores	Mean (SD)	65.4 (21.50)
	CLUE Comfort Scores		67.9 (21.50)

SD=Standard Deviation

*Summaries for the primaiy safety endpoints were provided for the safety population; all available data was included

**Summaries for primary efficacy and seconda1y endpoints were provided for the per-protocol population at the 1-week follow-up evaluation.

Clinical Study Protocol

CR-6521, v 3.0

■ JJV C CONFIDENTIAL

**Clinical Study Protocol
Johnson & Johnson Vision Care, Inc.**

Co-Primary Safety Endpoint Sample Size Calculations:

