14.3. Analysis Populations

Safety Population:

All subjects who are administered any test article excluding subjects who drop out prior to administering any test article. At least one observation should be recorded.

Per-Protocol Population:

All subjects who successfully complete all visits and do not substantially deviate from the protocol as determined by the trial cohort review committee prior to database hard lock. Justification for the exclusion of subjects with protocol deviations from the per-protocol population set will be documented in a memo to file.

Intent-to-Treat (ITT) Population:

All randomized subjects regardless of actual treatment and subsequent withdrawal from the study or deviation from the protocol. At least one observation should be recorded.

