14.5. Primary Analysis

Methodology regarding the plan for testing and/or handling statistical associations between co-primary safety and/or efficacy endpoints will be documented in the SAP.

Co-Primary Safety Analyses:

All primary safety analysis will be conducted on the safety population.

Grade 3 or Higher SLF

Grade 3 of Higher SLFs will be analyzed using a Bayesian beta-binomial model with correlated binary data.⁸

The Model:

Let \mathbb{Y}_1 and \mathbb{Y}_2 denote the binary outcomes of lens fit acceptance (Yes/No) in left and right eyes, respectively, across dispensing and follow-up visits when wearing the test lens. Considering the correlation, $\rho\rho$, between \mathbb{Y}_1 and \mathbb{Y}_2 , the distribution of the sum $YY = \mathbb{Y}_1 + \mathbb{Y}_2$ is obtained by the mixture of two variables. One of them follow a binomial distribution $BB\BBB(2, \rho\rho)$ with mixing probability $(1 - \rho\rho)$ and the other one follows a modified Bernoulli distribution, $MMBB\BBB(1 - \rho\rho)$, taking value 0 and 2 rather than conventional 0 and 1, with mixing probability $\rho\rho$:

$$PP(YY = yy | \rho\rho, \rho\rho) = (1 - \rho\rho)BB\BBB(2, \rho\rho)I_{AA1} + \rho\rho MMBB\BBB(1 - \rho\rho)I_{AA2},$$

where $I_{AA1} = \{0, 1, 2\}$, $I_{AA2} = \{0, 2\}$ and $\rho\rho$ is the probability of success (i.e., acceptable lens fitting).

To overcome the complexity of the mixture likelihood a latent variable ZZ_{ii} , $i = 1, 2$ is introduced in the model to indicate in which component of the model the observation yy_{ii} , $i=1, 2$, belongs to, that is,

$$ZZ = \begin{cases} 1, & \text{if the observation belong to the MBern}(p), \\ 0, & \text{if the observation belong to the Bin}(2, p) \end{cases}$$

The joint distribution of the augmented data (YY_{ii}, ZZ_{ii}) , $BB = 1, 2$, is given by

$$P(Y = y, Z = z | p, \rho) = \rho^{z_i} p^{y_i z_i / 2} (1 - p)^{(2 - y_i) z_i / 2} (1 - \rho)^{1 - z_i} \prod_{i=1}^2 p_{y_i}^{y_i(1 - z_i)} (1 - p)^{(2 - y_i)(1 - z_i)}$$

The probability p links to the regression variables through a logit transformation as follow:

$$\text{logit}(p) = \beta_0 + \beta_1 \text{lens}$$

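### Step 1.21 discontinues subjects on the reading that scores a failure for hypothesis 3, and 14.5 names no efficacy population; on the per-protocol set the hypothesis would almost certainly be met whatever the true rate

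*Combined protocol and SAP*

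**What the plan says.** **Endpoint.** Section 2.2 defines success as stability with blink of 5° or less and fixes the time point: "However, rotational stability assessed at least 15 minutes after lens insertion at the fitting visit is the primary endpoint". Under 2.3 and 14.5, hypothesis 3 is met if the lower 95% limit for the test lens is above 80%.

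**Exit rule.** In section 7.2, step 1.20 requires at least 15 minutes of settling. Step 1.21 then records stability and calls the toric fit unacceptable if absolute rotation exceeds 20° or if "The LENS STABILITY WITH BLINK is greater than 5 degrees". The consequence is stated there: "If one or both lenses demonstrate an unacceptable toric fit, the subject will be discontinued (proceed to final evaluation". For the second fitting, at Visit 3, "The steps followed will be the same as those listed under Visit 1: Lens Fitting #1". Section 8.2 lists the matching withdrawal reason: "Subject not successfully dispensed due to lack of efficacy and safety including poor vision, poor comfort, or unacceptable fit".

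**Populations.** Section 14.3 defines the per-protocol set as "All subjects who successfully complete all visits and do not substantially deviate from the protocol". The ITT set keeps randomised subjects whether or not they withdraw. For the safety co-primaries 14.5 is explicit: "All primary safety analysis will be conducted on the safety population". It has no matching sentence for efficacy.

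**Lens changes.** Step 1.24 allows up to two modifications per eye, with the settling and toric assessment repeated each time.

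**The concern.** The failure criterion of the endpoint and the criterion for leaving the study are the same event. A subject with an eye above 5° does not complete all visits and so is outside the per-protocol set. If hypothesis 3 were tested there, the failures would have been filtered out before the test began.

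The per-protocol set is a live option. Section 10 refers to a per-protocol analysis population. The sample size in 14.2 is expressed in completers. The Table 8 footnote records that the historical summaries for the efficacy "endpoints were provided for the per-protocol population at the 1-week follow-up evaluation".

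The protocol has already settled the parallel case. General lens fit also leads to discontinuation at its own failure criterion (step 1.22), but that co-primary is assigned to the safety population, so its failures are counted. Hypothesis 3 lacks that protection.

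All co-primaries must be met for the study to succeed, so at stake is whether one of them can tell a stable lens from an unstable one. The choice is left to a SAP that need only be final before database lock, while under 5.2 sponsor personnel know which lens is which.

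A second gap applies on any set. With two modifications allowed, an eye can have up to three settled readings, and the protocol does not say which one is scored.

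**Working it through.** **Inputs.** From the protocol: threshold 80% and lower 95% limit (14.5); planned rate 98% and between-eye correlation 0.70 (14.2); enrolment target 180 and 10% dropout (synopsis). Assumption: about 180 subjects are fitted with the test lens. If 180 are randomised 1:1 and the control lens passes at an assumed 98%, the figure is 90 + 90 × 0.974 = 177.7.

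**1. The plan's own figure.** Table 9 gives 99% power for stability with 100 subjects. Simulating 5,000 trials of the correlated-binomial model at 98% and correlation 0.70 gave 100.0% under each of three priors. This agrees with the statement in 14.2 that at least 99% of intervals clear 80%.

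**2. Who survives step 1.21.** Under that model, P(both eyes pass) = 0.3p² + 0.7p.

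- p = 0.80: 0.192 + 0.560 = 0.752, so 24.8% are discontinued
- p = 0.85: 0.217 + 0.595 = 0.812, so 18.8%
- p = 0.90: 0.243 + 0.630 = 0.873, so 12.7%
- p = 0.98: 0.288 + 0.686 = 0.974, so 2.6%

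**3. The test on survivors.** If step 1.21 is followed, the per-protocol set has no failing eye. With zero failures in n subjects, and the subject as a conservative unit, the exact lower limit is 0.025^(1/n).

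- n = 16: 79.4%; n = 17: 80.5%. Any set of 17 or more clears the threshold.
- At p = 0.80, 180 × 0.752 ≈ 135 remain. After a further 10% dropout about 122 remain, with a lower limit of 97.0%.
- On the eye scale, with 134 subjects: 0.025^(1/134) = 0.973, and solving 0.3p² + 0.7p = 0.973 gives p ≈ 0.979.

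**4. The test on all fitted eyes.** Two simulations used the same eye model: a 95% logit interval with subject-clustered standard error (178 subjects), and the Bayesian interval under three priors (180 subjects; 165 in the 98% row).

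| True rate | Per-protocol set | All fitted, clustered interval | All fitted, Bayesian interval |
|---|---|---|---|
| 80% | about 100% | 2.1% | 1.7-3.6% |
| 85% | about 100% | 44% | 45-50% |
| 90% | about 100% | 98% | about 99% |
| 98% (planned) | >99% | >99.9% | 100.0% |

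The entry that matters is the first row. A rule with nominal error near 2.5% at the threshold becomes one that passes essentially always.

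**5. Orientation (hypothesis 2).** Discontinuation is above 20° and failure is above 10°, so readings between the two cuts stay in. If rotation is roughly normal with P(|r| ≤ 10°) = 0.80, the SD is 7.8° and P(|r| ≤ 20°) = 0.990. The pass rate among retained eyes is 0.80/0.990 = 0.808, so the effect is minor.

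**The case against.** The strongest reply is that nothing in the protocol assigns hypothesis 3 to the per-protocol set. The wording closest to the test points the other way: 14.1 uses each subject's or eye's results where they exist, 2.3 counts lens fits, and 14.5 refers to eyes wearing the test lens. The list of populations in 14.1 concerns summaries. The Table 8 footnote describes past data at the 1-week visit, a different time point from this endpoint. A stand-alone SAP, not among the documents, may name the population. All of this stands. It makes the problem conditional, but none of it names an analysis set.

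A reader might infer that hypothesis 3 cannot fail. The documents do not support that, even on the per-protocol set. Step 1.24 permits modification for other reasons, so a site might refit an unstable lens and keep the subject. If the first lens were scored, that failure would remain in the set. A site could also continue a subject in error. With no failures the logit mixed model gives no usable interval, and the Bayesian alternative in 14.5 is only a possibility, with its details deferred.

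It is also fair that the contrast needs a lens far below expectation. At a true 80%, the loss of 24.8% of fitted subjects would show in the disposition table, and about 134-135 retained subjects fall short of the 144 required and the 165 targeted unless others are added, as 4.3 and 8.2 allow. Visible loss would alert a careful reader but would not change the formal result of the test.

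**Conclusion.** The point holds in conditional form. The exit rule and the failure criterion coincide, and the protocol does not name the efficacy population. If the per-protocol set is chosen, hypothesis 3 is almost certain to be met whatever the true rate: about 100% against about 2-4% at a true 80%. On the ITT or safety set, or if all available readings are used as 14.1 suggests, the failing readings count and the test behaves normally. At the planned 98% the choice makes no practical difference.

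The figures assume that step 1.21 is followed, correlation 0.70, about 178-180 test-fitted subjects, and a zero-failure method that behaves like an exact or Bayesian interval.

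This is a gap to close before the SAP is final. It is not evidence that the sponsor has chosen the favourable set. A reader might extend the argument to CLUE Vision through the dispensing criteria in step 1.29. The documents give neither the number of subjects who would reject the lens nor their scores, so that effect cannot be sized, and no change is proposed there.

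**What to change.** Keep the clinical procedures and add to 14.5, with the same text in the SAP:

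*Toric orientation and rotational stability (hypotheses 2 and 3) are analysed on every eye fitted with the test lens, including eyes of subjects discontinued at the fitting visit. If a lens is modified, the settled reading (15 minutes or more) of the first test lens is scored.*

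Scoring the first lens is one reasonable choice; what matters is fixing the choice in advance. If the dispensed lens is preferred, add that a subject who is never dispensed contributes the last settled reading taken.

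The cost is wording only, because step 1.21 already records the failing readings. Observed rates may be slightly lower than among completers. Power on all fitted eyes stays above 99% at the planned 97.5% (orientation) and 98% (stability) with 165-180 subjects.

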7.3. Unscheduled Visits

If, during the investigation, a subject requires an unscheduled visit to the clinical site, the following information will be collected, as appropriate:

- Chief complaint prompting the visit. If the reason is an adverse event, the applicable eCRF for the adverse event must be completed and subject record completed as appropriate.
- Date and time of the visit and all procedures completed at the unscheduled visit.
- Review of adverse event and concomitant medications.
- Documentation of any test article dispensed or collected from the subject, if applicable.
- Slit lamp findings (using the Slit Lamp Classification Scale).

If the Investigator withdraws a subject from the study, the final study visit case report forms must be completed indicating the reason(s) why the subject was withdrawn. The subject record must be completed documenting the date and primary reason for withdrawal and the study CRA notified.

Any ocular and non-ocular Adverse Events that are ongoing at the time of the study visit will be followed by the Investigator, within licensure, until they have resolved, returned to pre-treatment status, stabilized, or been satisfactorily explained. If further treatment i.e., beyond licensure is required, the subject will be referred to the appropriate health care provider.

The following information will be collected during an unscheduled visit.

Clinical Study Protocol
Johnson & Johnson Vision Care, Inc.

Unscheduled Visit		
Ste	Procedure	Details
U.1	Reason for unscheduled visit	Indicate if the only reason for the visit is that the subject requires additional test articles. If the reason is other than resupply of previously dispensed lenses, specify the reason for the visit.
U.2	Chief Complaints (if applicable)	Record the subject's chief complaints for reasons for the unscheduled visit.
U.3	Adverse Events and Concomitant Medications Review (if applicable)	Review any changes to the subject's medical history or concomitant medications from the previous study visit. Record any changes, and any adverse events.
U.4	Entrance VA (if applicable)	Record the entrance distance visual acuity (OD, OS) to the nearest letter.
U.5	Subjective Spherical-cylindrical Refraction (if applicable)	Perform bare-eye subjective spherical-cylindrical refraction with a phoropter (adopt the maximum plus to maximum visual acuity (MPMVA) approach and use the duo-chrome test for binocular balancing) and record the best corrected distance visual acuity to the nearest letter OD, OS.
U.6	Slit Lamp Biomicroscopy (if applicable)	FDA Slit Lamp Classification Scale will be used to grade the findings. If the clearance of the fluorescein needs to be expedited, preservative-free rewetting drops may be instilled.
U.7	Dispensing (if applicable)	If the subject requires additional lenses to complete the wear period and is eligible to do so, provide additional lenses per the dispensing instructions given in the detailed study procedures.
U.8	Exit Visual Acuity (if applicable)	Record the subject's exit distance visual acuity (OD, OS to the nearest letter).

NOTE: If the only reason for the unscheduled visit is that the subject requires additional test articles, only the dispensing information needs to be recorded.

